A Preliminary Investigation of Pre-Frontal Repetitive Transcranial Magnetic Stimulation (rTMS) for the Treatment of Cannabis Use Disorder

Statistical Analysis Plan

NCT03144232

June 27, 2023

We calculated descriptive statistics such as means and standard deviations (SD) for all continuous variables and proportions for categorical variables. We compared demographic, screening, blinding, and adverse event variables (compiled using MEDdra criteria) across condition and site using t-tests or the Wilcoxon Rank Sum test for continuous variables and the Chi-Square or Fisher's Exact test for categorical variables.

For Aim-1, we utilized a generalized linear mixed-effects model (GLMM) to perform the analyses, with the full ITT sample (N=72) and the total MCQ-SF score as the dependent measure. We used two types of a priori models for each analysis: 1) a three-way interaction model which included an interaction between treatment, site, and time, as well as the main effects of treatment, site, time, and all pairwise interactions between the main terms, and 2) a two-way interaction model which included treatment, time, an interaction between treatment and time, and site. We considered pre- and post- variables with a strong clinical rationale for inclusion in covariate adjustment including the amount of time since the last cannabis use, CWS score, the days-per-week of cannabis use, the grams of cannabis used per day, and the number of cannabis use sessions per day.

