To assess group differences in the number of weeks of abstinence in the follow-up period (Aim-2a), a Poisson regression model was fit with the total number of weeks of self-reported abstinence in the four-week follow-up period as the dependent variable and treatment, site, and treatment by site interaction as independent variables. We conservatively imputed missing values as non-abstinent, thereby including the total ITT sample. We additionally performed a sensitivity analysis for weeks of abstinence by including the weeks preceding the 9th rTMS-treatment visit and immediate post-visit since these two weeks represent the time following the delivery of a total of 16-sessions of rTMS (a similar dose to early rTMS for depression studies). We calculated the relative risk of having a week of abstinence as a measure of the effect size, along with 95% confidence intervals. We used creatinine-corrected urine cannabinoids to verify self-reported abstinence at follow-up weeks 2 and 4, and calculated the proportion that these two methods were concordant.

To evaluate group differences in the number of days of cannabis use (Aim-2b), we utilized a GLMM with the number of days-per-week of cannabis use as the dependent measure. We included participants in the model who had follow-up data (the completer sample; N=51) and given the apparent divergence in days-per-week of cannabis use in the final two-weeks of the follow-up period, we chose to focus our analysis on that period.

Residual normality was assessed for each of the above models using QQ-plots. We included sex in all models to detect a potential effect, but when no significant effects were found, we excluded sex from the subsequent final models. Apart from craving, this was a pilot trial and not powered a priori to detect statistically significant differences; however, statistically significant *p*-values are noted when observed. When reported, a level of $\alpha = 0.05$ was used (two-tailed), and no adjustments for multiple comparisons were made for this preliminary investigation. Effect sizes at each time point were estimated as Cohens d using means and pooled standard deviations. Statistical analyses were conducted using R software (version 4.2.1, GNU project) and SAS version 9.4 (Cary, NC).

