Statistical Analysis: Baseline demographic and clinical measures will be compared across treatment groups using standard statistical methods (i.e., categorical variables compared using Pearson chi square test of independence; continuous variables compared using univariate ANOVAs). Characteristics that display imbalance at the baseline measure, association with the dependent variable, or are known to be predictive of cue induced craving, reactivity, or cannabis-use outcomes will be assessed for inclusion as covariates in the final models. To test our primary hypothesis that a full course of active excitatory rTMS will reduce cue induced craving as compared to sham rTMS (Aim 1), generalized linear mixed effects models will be constructed to estimate treatment group differences in craving scores. Overall statistical significance for the effects of treatment group, time, and their interaction will be assessed using a likelihood ratio test that compares the final model, to a model consisting of an intercept term alone. The hypothesis that those receiving active rTMS will have decreased craving will be tested using model-based estimates to construct group level comparisons across all the planned time points. Normality of residuals will be tested for these models and when found in error, appropriate transformations or non-parametric methods will be conducted. For Aim 2 (evaluating the impact of rTMS on cannabis CR), BOLD response during the cannabis cue vs. neutral cue trials will be the primary contrast of interest to test hypotheses. Where significant differences are observed, parameter estimates from task-based models, from each ROI will be extracted and relations with clinical endpoints examined. For our exploratory Aim: The primary analysis will involve preliminarily investigating the efficacy of active rTMS, compared to sham rTMS in increasing the proportion of cannabis abstinent participants during the final two weeks of study treatment (four-week follow-up). A combination of self-reported abstinence from

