Sample Size Justification: The primary focus of this study is to show evidence, with sufficient strength, that treatment with active rTMS will result in decreased cue induced craving (Aim 1), and decreased BOLD response in reward network structures during a cue-reactivity fMRI paradigm (Aim 2) in CUD participants treated with either active or sham rTMS. For Aim 1: Within subject craving measures tend to be highly correlated when measured closely in time and thus we assume a conservative ICC of $p=0.75$ (previous CUD studies range $p=0.60-0.75$) with a standard deviation of ≈ 12.2 . We intend to detect a clinically meaningful craving score difference between the two treatment groups of 8.5 (Cohen's $d=8.5/12.2\approx 0.7$). This is a conservative estimate given that recent multi-session rTMS treatment trials have yielded larger effect sizes on craving ($d=0.98$ (7) in alcohol users, and $d=0.84$ (9) in cocaine users). In the proposed study we will measure increased craving (via MCQ total score) following the presentation of a validated cannabis cue paradigm both before and after a treatment course of rTMS. Under the assumption of independent observations, a total sample size of 32 participants equally allocated to each treatment assignments will provide 80% power with a type 1 error rate of 5% to detect the stated effect size of 0.7. However, the effective sample size in a repeated measures data setting is reduced when assuming an ICC of 0.75. The number of participants per group required is therefore estimated to be $n=27$. Additionally, we need to adjust for study attrition between randomization and the 4-week follow up visit. Assuming an attrition rate of up to 25%, a sample size of **36 participants randomized to each treatment group (n=72 total)** will provide adequate power to detect the primary aim effect size of $d=0.7$ between those receiving active and sham rTMS. **For Aim 2:** In a within subjects investigation of nicotine use disordered participants undergoing a single session of rTMS, there was a significant effect on BOLD response to smoking cues (see figure 2, Preliminary Studies section). If we assume that, as with previous study of cue induced BOLD reactivity in smokers using rTMS, our effects are of medium to large size (e.g. $d=0.7-0.8$) with alpha =5% (2-tailed), a sample of **36 randomized participants in each group will result in greater than 80% power for detecting effects of treatment on CR-BOLD response**. In sum, we are confident that the proposed randomized sample size of 72 participants will be sufficient to test Aims 1 and 2. **For our exploratory Aim**, our recent, non-contingency management based medication trials for cannabis cessation have shown varying placebo abstinence rates (defined as ≤ 50 ng/ml THCCOOH UCT) at the end of study (EOS) treatment (5-15%) (38, 39, 41). Since we are only hoping to provide preliminary data to power a more definitive study, our sample is not designed to sufficiently answer this question definitively. Despite this fact we will still have power to detect a large effect on abstinence. An rTMS abstinence rate of at least 30% greater than placebo at the end of study treatment under the most conservative conditions, at a 10% placebo abstinence rate, a randomized sample size of 36 participants in each treatment group will provide 80% power with a type 1 error of 5% to detect this difference at the end of this pilot study.

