
Relapse, Drop-Out and Clinical Deterioration: Every effort will be made to re-engage participants who miss appointments. Clinical deterioration, such as exacerbation of psychiatric or substance use disorder, will be assessed on a case-by-case basis by [name] and appropriate referral will be made. Participants will be considered dropouts if they do not come back to treatment after receiving three phone calls. A last observation carried forward will be used for each outcome in participants who formally withdraw from the study or stop participating.

Strategies to ensure a robust and unbiased approach: The proposed study will achieve robust and unbiased results via several design features including: explicit inclusion/exclusion criteria; randomization of treatment condition; the use of a validated sham control; blinding; use of validated laboratory and interview/self-report measures and methods; explicit hypotheses and corresponding planned statistical analyses; power estimates; planned handling of retention/attrition and missing data; and careful consideration of potential confounds. All experimental details are reported in a detailed and fully transparent manner to support replication.

Consideration of gender as a biological variable: Though this trial is not powered to detect gender differences, we will perform our analysis using gender as a potential covariate, and should there be a potential gender difference found, we will be able to use that data to power a larger trial.

E. PROTECTION OF HUMAN SUBJECTS

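### The protocol's carry-forward rule for every outcome was never withdrawn, conflicts with the SAP's own rules, and can bias the craving contrast

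*Combined protocol and SAP*

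**What the plan says.** Four rules or silences stand side by side.

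- **Protocol, Section D, Relapse, Drop-Out and Clinical Deterioration:** "A last observation carried forward will be used for each outcome in participants who formally withdraw from the study or stop participating". The preceding Missing Data and Attrition paragraph covers preventing loss and continuing assessments. It gives no analytic rule.
- **Craving (Aim 1):** the protocol's Statistical Analysis section says "generalized linear mixed effects models will be constructed to estimate treatment group differences in craving scores". The SAP fits the model "with the full ITT sample (N=72) and the total MCQ-SF score as the dependent measure". Neither says how a missing value is treated.
- **Weeks of abstinence (SAP, Aim-2a):** "We conservatively imputed missing values as non-abstinent, thereby including the total ITT sample".
- **Days of use (SAP, Aim-2b):** "We included participants in the model who had follow-up data (the completer sample; N=51" of 72 randomised.

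The SAP never mentions carrying values forward, and no text says that its rules replace the protocol's.

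The measurement schedule also matters. The full cue paradigm is run twice, before the first and after the last treatment (rTMS Sessions). The scan is done twice, before the first and before the final treatment (fMRI Paradigm). The MCQ is taken around every cue exposure (assessment schedule), and physical cues are shown at each session.

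**The concern.** With only two full-paradigm assessments, someone lost between them has one value to carry: baseline. The filled-in change is then zero, whatever would have happened. The same holds for a missing second scan under the protocol's Aim 2. Filled-in values enter the analysis as though they had been measured, and the mixed model no longer works from the observed data alone.

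Two things are at stake. The craving estimate can be wrong in size, and a difference in dropout between arms can look like a treatment difference. Separately, an analyst holding both documents could treat the same lost participant in different ways and claim support for each.

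**Working it through.** **Inputs from the Sample Size Justification.** The target is "a clinically meaningful craving score difference between the two treatment groups of 8.5", "with a standard deviation of ≈ 12.2", within-subject correlation 0.75, attrition up to 25%, 36 per arm. The two-sided 5% level is from the SAP.

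**The plan's own figure.** Independent observations: n = 2 × (1.96 + 0.842)² × 12.2² / 8.5² ≈ 32.3, so 33 per group against the stated 32. Correlation step with three measures: 32 × (1 + 2 × 0.75) / 3 = 26.7, so 27 as stated (two measures give 28). Attrition: 27 / (1 − 0.25) = 36. The plan's figure is reproduced to within one participant.

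**Size of the carry-forward effect.** Let δ be the true difference in improvement, T the improvement common to both arms, and dA and dS the fractions of active and sham lost before the final visit. With baseline carried, the expected difference is

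(T + δ)(1 − dA) − T(1 − dS) = δ(1 − dA) + T(dS − dA).

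The change-score SD is 12.2 × √(2 × (1 − 0.75)) = 8.63. Rejection rates come from simulated trials with 36 per arm, random dropout and a t-test on change. The comparator is the same test on observed changes only.

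The values of T, the 15%/35% split and the timing of loss are assumptions; the documents give none of them.

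| δ | T | dA / dS | Expected difference | Rejection, carried | Rejection, observed |
|---|---|---|---|---|---|
| 8.5 | 0 | 25% / 25% | 8.5 × 0.75 = 6.4 | 93% | 94% |
| 8.5 | 8.5 | 25% / 25% | 6.4 | 81% | 94% |
| 8.5 | 8.5 | 12.5% / 12.5% | 8.5 × 0.875 = 7.4 | 92% | 97% |
| 8.5 | 8.5 | 35% / 15% | 5.5 − 1.7 = 3.8 | 37% | 94% |
| 8.5 | 8.5 | 15% / 35% | 7.2 + 1.7 = 8.9 | 98% | 94% |
| 0 | 0 | 15% / 35% | 0 | 5% | 5% |
| 0 | 4 | 15% / 35% | 0.8 | 7% | 5% |
| 0 | 8.5 | 15% / 35% | 1.7 | 14% | 5% |
| 0 | 8.5 | 25% / 25% | 0 | 5% | 5% |

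The 12.5% row is the 25% allowance with half the losses after the final visit. With no true effect and the split reversed, the spurious difference has the same size and favours sham. In every scenario the observed-data estimate stays at about the true value.

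**Loss actually reported.** 72 − 51 = 21 participants (29.2%) lacked follow-up data. If all 21 had also missed the final visit, equally by arm, 8.5 would become 8.5 × 51/72 = 6.0. The documents give neither the timing nor the split by arm.

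**Abstinence.** Take a participant whose last reported week was abstinent and who is then lost. For the SAP's count of self-reported weeks, carry-forward scores the remaining weeks abstinent and the SAP scores them non-abstinent. For the protocol's composite, a carried week-2 urine value gives a four-week to two-week ratio of 1.0. That fails the < 0.5 criterion, so both rules give non-abstinent.

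**The case against.** The strongest reply is that the later SAP, written in the past tense, shows no use of carry-forward. Its absence there suggests that the rule was dropped. That is plausible, but it is nowhere stated, and for craving the SAP names no rule that could have replaced it.

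A reader might infer that the protocol contradicts its own mixed model. The documents do not support this. Neither says that the model relies on observed data under missing at random, and a mixed model can be fitted to filled-in data. What stands is that carry-forward defeats the model's main advantage and that craving is left without a reconciled rule.

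A reader might also infer that every dropout is given zero change. That is not established. MCQ values exist from session cues, and the protocol does not say whether one of those or the baseline paradigm value is carried. Anyone lost after the final visit already has a post-treatment value. The 25% allowance runs to the four-week follow-up, so applying all of it before the final visit is the unfavourable end of the range.

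Nor is bias unconditional or always towards no effect. With equal dropout and no true effect there is none. With no common trend, power barely moves. With sham losing more, the estimate is 8.9, close to the truth.

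Finally, if people who stop treatment gain nothing, 6.4 could be the effect in all randomised participants. That is a legitimate target, but it should be declared as such and not arise from a fill-in rule. Missing at random is itself untestable, which is why a sensitivity analysis is needed.

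**Conclusion.** The point holds in a conditional form. The protocol contains a stated rule that can give a wrong craving result. The SAP departs from it for weeks of abstinence and days of use without saying so, and is silent for craving. The abstinence conflict concerns the SAP's self-reported weeks only; extending it to the protocol's urine-ratio composite would be wrong.

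All the sizes assume random dropout, and that baseline is carried for anyone lost before the final visit. Under equal loss totalling 25%, the planned 8.5 points shrinks to between 6.4 and 7.4. If all of that loss precedes the final visit, power is 81% to 93% against 94% on observed data. Larger distortions, and any false-positive inflation, require both a common improvement and dropout that differs by arm. The documents do not show whether either occurred, so these figures do not show that the reported craving result is biased.

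**What to change.** Delete the carry-forward sentence, or state in the SAP that it is superseded, and give one rule per outcome:

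- **Craving:** a likelihood-based mixed model on all observed visits of all 72 randomised participants, with missing at random stated as an assumption. Add one sensitivity analysis that shifts the unobserved values by an arm-specific delta.
- **Days of use:** the same type of model on all observed visits of all 72, in place of the completer set. It must include earlier weeks, or participants without follow-up contribute nothing.
- **Abstinence:** keep missing as non-abstinent, for this outcome only.

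Report the number lost before and after the final visit, by arm, so that a reader can place the trial within the range above.

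The cost is wording in two documents and one extra run. No new data are needed, and the sample size does not change because 27 / 0.75 = 36 already allows for lost endpoints.

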1. RISKS TO THE SUBJECTS

Targeted/Planned Enrollment Table

Total Planned Enrollment 72 (Randomized)

TARGETED/PLANNED ENROLLMENT: Number of Subjects			
Ethnic Category	Sex/Gender		
	Females	Males	Total
Hispanic or Latino	1	3	4
Not Hispanic or Latino	4	4	68
Ethnic Category: Total of All Subjects*	72		
Racial Categories			
American Indian/Alaska Native	0	0	0
Asian	1	2	3
Native Hawaiian or Other Pacific Islander	1	1	2
Black or African American	8	17	25
White	12	30	42
Racial Categories: Total of All Subjects*	22	45	72

We will attempt to recruit all potential participants from the community. We will not exclude anyone based on gender, ethnicity, or race. The above estimated enrollment numbers are based on our experience with this clinical population. We have randomized a total of 43 participants at MUSC, and so plan on randomizing an additional 28 participants at Stanford. Assuming two participants will be lost to follow-up between an enrollment visit and randomization visit, we plan on enrolling a total of 30 additional participants at Stanford to randomize 28.

Compensation and Retention: Participants will be compensated based upon attending visits as well as given additional compensation using a contingency management paradigm. Participants will be given \$40 for their baseline visit. Participants will then be compensated \$25 for each rTMS/BMDC visit they attend during the acute treatment phase (10 visits), \$80 for attending the two-week follow-up visit, and \$100 for attending the four-week follow-up visit. Additionally, “fishbowl” contingency management will be used (an average of \$175, a minimum of \$78, and a maximum of \$350) for participants who attend all appointments in order). For “fishbowl” contingency management, participants who present at their scheduled visits will receive chances to draw from a bowl containing 250 chips that are assigned a certain value (230 chips denote \$1, 18 chips denote \$10, one chip denotes \$50, and one chip denotes \$100). Participants will start with one draw on the first TMS visit and the number of token picks will increase by 1 for every scheduled visit attended including follow up visits. If participants miss a scheduled visit, then token picks will start back at 1 token, and the process repeats. If completing all visits and assessments, participants could potentially receive a total of \$645. Participants will be

compensated at the end of each visit, and thus will receive pro-rated compensation as they complete the study.

There will be no additional compensation for those choosing to receive open label treatment following the experiment.

b. Sources of Materials

Assessments:

Data collection:

Schedule of visits and assessments and Data Collection:

	Assessment domain	Screen	Baseline	Final rTMS Visit	2-week F/U	4-week F/U
Screening and Enrollment Eligibility:						
MINI International Neuropsychiatric Interview (MINI) for the DSM-5 (54): Structured interview to determine DSM-5 based psychiatric conditions.	Psychiatric history	X				
Urine Pregnancy Test (bHCG)	Pregnancy status	X				
Hamilton Rating Scale for Depression 24-Item (HRSD₂₄)(55): Clinician administered measure of depressive symptoms.	Depressive symptoms	X		X	X	X
The Cannabis Use Disorder Identification Test-R (CUDIT-R)(56): Validated measure assessing severity of disordered cannabis use.	Severity of Cannabis Use	X				
Cannabis Cue-Induced Craving (Aim 1): Primary outcome: Change in MCQ score during cannabis cue paradigm. Secondary outcome: Average weekly change in MCQ assessed during each TMS treatment session.						
The Marijuana Craving Questionnaire (MCQ) (57): Validated measure of cannabis craving. Collected before and after each cannabis cue exposure.	Provoked Cannabis Craving		X	X	X	X
Activation of Reward Structures (Aim 2): Primary outcome: Percent signal change in BOLD response during cue-reactivity fMRI paradigm.						
Substance Use Outcomes (Exploratory Aim): Primary outcome: Number of participants who are abstinent by TLFB for the last 2 weeks of the study with a ratio of four-week to two-week creatinine corrected urine THCCOOH of <0.5. The THCCOOH ratio is able to accurately predict no new cannabis use (10-12).						
Secondary outcomes: change in a) creatinine corrected cannabis level (ng/ml) and; b) subjective use measured by TLFB (number of days used per week and number of cannabis use sessions per week).						
Time Line Follow Back (TLFB) (58): Calendar-based instrument designed to assess substance use.	Self-Reported Substance Use	X	X	X	X	X
Urine Drug Test with Creatinine Corrected Cannabis Level (Collected on the 1st, 5th and 10th rTMS visit, and at follow-up visits)	Objective Substance use	X	X	X	X	X

Delayed Discounting Task (67): Participants choose between receiving hypothetical money immediately or more money if they wait longer.	Cognitive Control		X	X		
Cannabis Withdrawal Scale (59): Validated questionnaire that looks at symptoms of withdrawal.	Cannabis Withdrawal		X	X	X	X

PROTECTION OF HUMAN PARTICIPANTS

